6.4.3 Net Acid Resistance test

To test whether the dentifrice imparts acid resistance to the enamel after 14 days of intra-oral exposure, a second in vitro demineralization will be repeated following the same protocol as described above on the two human and two bovine enamel specimens. SMH will be then evaluated by placing 5 indentations 100 µm to the right of the indentations placed in situ remineralization (See Figures 2 and 3). The %NAR will be calculated by the method of Corpron [Corpron et al., 1986]:

$$\% \text{ Net Acid Resistance} = [(D1-D2) / (D1-B)] * 100$$

B= Indentation length (µm) of sound enamel at baseline

D1= Indentation length (µm) after first in vitro demineralization

D2= Indentation length (µm) after second in vitro demineralization

Acid resistance is indicative of any protection that the treatments and intra-oral exposure may afford the enamel specimens. The net loss of enamel due to clinical caries is the result of multiple cycles of demineralization and repair (remineralization). It is well established that repaired enamel is more resistant to subsequent acid challenges.

6.4.4 Comparative Acid Resistance test

This measure takes a different approach to understanding whether the enamel formed during remineralization is more resistant to acid than the original enamel. Using the data from the four centrally located enamel specimens, the equation used will compare explicitly the reduction in SMH brought by the first and second acid challenges:

$$\% \text{ Comparative Acid Resistance} = [(D2-R) / (D1-B)] * 100$$

B= Indentation length (µm) of sound enamel at baseline

R= Indentation length (µm) of enamel after in situ remineralization

D1= Indentation length (µm) after first in vitro demineralization

D2= Indentation length (µm) after second in vitro demineralization

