2. STUDY DESIGN

This will be a double blind, single center, 4-way crossover design study. Two to three days before the start of each treatment period the subjects will have their teeth cleaned to remove all accessible plaque and calculus and will be provided with a non-fluoride

dentifrice to use until their next visit. At the beginning of each testing period, two gauze-covered 4 × 4 mm partially demineralized human enamel specimens will be placed in the buccal flange area of the subject’s mandibular partial denture. In addition, two gauze-covered 4 mm round partially demineralized bovine enamel specimens will be placed in the buccal surface of two posterior denture teeth of the same side of the partial denture. Once specimens are placed, subjects will wear their partial dentures twenty-four hours a day and use their assigned toothpaste twice daily, as instructed, until their next visit. Specimens will be removed after two weeks and the subjects will undergo a four to five day washout period followed by another cleaning and two to three day lead in period. This process will be repeated until all subjects have used all four test products. Changes in the mineral content of the enamel specimens will be assessed using the SMH and TMR. Enamel fluoride uptake (EFU) will be determined using the microdrill enamel biopsy technique. In addition the net acid resistance (NAR) and the comparative acid resistance (CAR) of the remineralized enamel specimens will be determined.

2.1 Study Schedule:

	Visit 1	Visit 2, 5, 8, 11	Visit 3, 6, 9, 12	Visit 4, 7, 10, 13
	Screening	Prophy	Begin Tx	End Tx
Informed Consent	X			
Medical history review	X	X	X	X
Oral Soft Tissue exam	X	X	X	X
Oral Hard Tissue exam	X	X (v2 only)		X (v13 only)
Salivary Flow	X			
Inclusion/Exclusion criteria	X	X		
Continuance Criteria		X	X	X
Randomization			X	
Adverse Event monitoring		X	X	X
Dental Prophylaxis		X		
Placement of specimens			X	
Removal of specimens				X
Issue washout tooth paste		X		
Return washout tooth paste			X	
Issue study products and diary			X	
Return study products and diary				X
Study close-out				X (v 13 only)

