6.4 Efficacy Measurements and Evaluations

6.4.1 Surface Microhardness

The SMH test will be used to assess changes in the mineral status of partially demineralized enamel specimens. SMH will be measured using a Wilson 2100 Hardness Tester. Each enamel specimen will be secured on a 1-inch square acrylic block with sticky wax and then placed on the microhardness tester. Five baseline indentations spaced 100 µm apart will be placed with a Knoop diamond under a 50 gram load in the center of a flattened, polished sound enamel specimen. SMH will be determined by measuring the length of the indentations using Wilson 2100 - Clemex CMT Software (version 6.0.011). For enamel specimens to be acceptable for use in the study, the mean of the five baseline indentation length must be $43 \pm 3 \mu\text{m}$ with a standard deviation of $\leq 3\mu\text{m}$.

After in vitro demineralization, the enamel specimens will be again SMH tested by placing five indentations 100 µm to the left of the baseline indentations (see Figures 2 and 3). To qualify for the study, the mean ($n = 5$) indentation lengths of the partially demineralized specimens must be $120 \pm 20 \mu\text{m}$ with a standard deviation of $\leq 10\mu\text{m}$. After 14 days of intra-oral exposure the enamel specimens will be again SMH-tested by placing five indentations 100 µm to the right of the baseline indentations (see Figure 2 and 3). The extent of remineralization will be calculated based on the method of [Gelhard et al., 1979].

$$\%SMH \text{ recovery} = (D1-R)/(D1-B) \times 100$$

B = indentation length (µm) of sound enamel specimen at baseline

D1 = indentation length (µm) after in vitro demineralization

R = indentation length (µm) after intra-oral exposure.

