7. STATISTICAL ANALYSES AND SAMPLE SIZE JUSTIFICATION

7.1 Statistical Analyses

The mean % SMH recovery will be calculated using the five sets of indentations within each enamel specimen. The mean fluoride uptake will be calculated using the four samples within each enamel specimen. The mean % SMH recovery, mean fluoride uptake, mean acid resistance and mean ΔZ , L, SZ_{max} will be computed for the two enamel specimens within a subject for each specimen location (buccal flange or tooth) by treatment; if a subject is missing an enamel specimen, the available enamel specimen will be used. Analyses of fluoride uptake will be performed after using a natural logarithm transformation because the measurements generally are not normally distributed. The validation of the new model will involve two types of evaluations. 1) Analysis level evaluation: The treatments will be compared using analysis of variance models (ANOVA) suitable for a crossover study. The models will include random effects for subject and fixed effects for study period, product, specimen location, and the location-by-product interaction. The random effects will model the correlation and variances over time within a location and the correlation between locations. The primary comparisons of interest will be to determine if the specimens placed in the tooth find the same comparisons to be statistically significant as the specimens placed in the buccal flange. In addition, although likely to be underpowered, the analyses will also include an evaluation of the equivalence of the two locations. This will involve calculating a 95% confidence interval for the ratio between the tooth and buccal flange locations for the relative difference between treatments (treatment difference divided by the positive control mean). A 5% significance level will be used for all tests. No alpha-level adjustments for multiple comparisons adjustments will be applied. 2) Data level evaluation: Agreement between the data from the tooth and buccal flange locations will be evaluated using Bland-Altman plots and intraclass correlation coefficients (ICCs).

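### Does %CAR, which rises as enamel gets softer despite its name, need to be redefined or dropped from the tested outcomes?

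*Combined protocol and SAP*

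**What the plan says.** Three indices are built from the same four indentation lengths: B (sound), D1 (after the first acid challenge), R (after intra-oral exposure) and D2 (after the second acid challenge).

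- 6.4.1: %SMH recovery = (D1-R)/(D1-B) x 100.
- 6.4.3: %NAR = (D1-D2)/(D1-B) x 100, measured "on the two human and two bovine enamel specimens".
- 6.4.4: %CAR = (D2-R)/(D1-B) x 100. Its purpose is "understanding whether the enamel formed during remineralization is more resistant to acid than the original enamel", and "the equation used will compare explicitly the reduction in SMH brought by the first and second acid challenges". The data source is given as follows: "Using the data from the four centrally located enamel specimens".

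Section 2 lists both acid-resistance indices: "In addition the net acid resistance (NAR) and the comparative acid resistance (CAR) of the remineralized enamel specimens will be determined". Section 7.1 has a single entry for them in its list of averaged outcomes: "mean fluoride uptake, mean acid resistance and mean". Section 7.1 makes agreement in statistical significance between the tooth and flange locations the primary comparison. It adds an equivalence evaluation based on the tooth/flange ratio of relative differences, each being "treatment difference divided by the positive control mean", and says in advance that this evaluation will probably lack power.

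**The concern.** Longer indentations mean softer enamel, so %CAR goes up as resistance goes down. Its name says the opposite, %NAR runs the other way, and the plan never says which end of the %CAR scale is favourable. A significant %CAR difference could be reported with the wrong sign or appear to contradict %NAR.

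Three further points add to this:

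- %CAR is fixed by the other two indices, so tooth/flange agreement on all three is not three separate pieces of validation evidence.
- The 7.1 ratio divides by the positive-control mean, and for %CAR that mean shrinks towards zero as the product protects better.
- The single term in 7.1 does not say which index is meant, and the description of the specimens as central fits neither the flange nor the tooth location.

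**Working it through.** **The plan's own figure.** Section 7.2 gives 80% power for a 6-point difference in %SMH recovery, with an SD of differences of 10, 24 completers and two-sided 5%. A paired t-test with noncentrality 0.6 x √24 = 2.94 on 23 df gives 80.4%, so the figure is reproduced. It concerns %SMH recovery only; no mean, SD or power is stated for %NAR or %CAR.

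**Direction.** Take B = 43 and D1 = 120 µm (the 6.4.1 targets), so D1-B = 77, and assume R = 90. As D2 goes from 90 to 140, %CAR rises from 0 to 50/77 = 64.9, while %NAR falls from 30/77 = 39.0 to -20/77 = -26.0. %CAR = 100 requires D2 = R + 77, meaning the second challenge softens as much as the first. Below 100 means more resistant than original enamel, which answers the question that 6.4.4 poses.

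**Identity.** [(D1-R) - (D1-D2)]/(D1-B) = (D2-R)/(D1-B), so %CAR = %SMH recovery - %NAR. It carries over to means if the same specimens supply all three; a missing D2 breaks it.

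**When the indices disagree.** From the identity, ΔNAR = ΔSMH recovery - ΔCAR. With lower %CAR read as better, the two indices rank products oppositely when ΔCAR lies between 0 and ΔSMH recovery; at the 6-point difference of 7.2, that is a ΔCAR between 0 and 6. An illustration with assumed R and D2:

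| Product | R | D2 | %SMH recovery | %NAR | %CAR |
|---|---|---|---|---|---|
| Placebo | 110 | 118 | 13.0 | 2.6 | 10.4 |
| Fluoride | 85 | 88 | 45.5 | 41.6 | 3.9 |
| Fluoride | 85 | 100 | 45.5 | 26.0 | 19.5 |
| Fluoride | 85 | 110 | 45.5 | 13.0 | 32.5 |

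The indices agree at D2 = 88 and disagree at 100 and 110. The disagreement window is D2 from 85 + 8 = 93 up to 118.

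**Effect on tests.** Replacing %CAR by 100 - %CAR changes the sign of every treatment difference and leaves its standard error alone. Two-sided p-values, and hence the tooth/flange matching, stay the same.

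**Effect on the ratio.** With the same treatment difference at both locations, the ratio reduces to the flange positive-control mean over the tooth mean. For assumed tooth/flange %CAR means of 20/16, 10/6 and 5/1, it is 0.80, 0.60 and 0.20. On the 100 - %CAR scale it is 84/80 = 1.05, 94/90 = 1.04 and 99/95 = 1.04. So the ratio does depend on distance from zero.

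How near to zero matters? A Fieller interval becomes unbounded when the tooth positive-control mean is below t(0.975, 23) x SD/√24 = 2.069 x 10/4.899 = 4.2 for an assumed SD of 10 (2.1 for SD 5, 6.3 for SD 15). Simulation with n = 24, true ratio 1, a 20-point difference, an assumed per-treatment SD of 15 and an SD of differences of 10 gives these central 95% ranges:

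| Positive-control mean | Central 95% range of the ratio |
|---|---|
| 40 | 0.69 to 1.44 |
| 20 | 0.63 to 1.58 |
| 10 | 0.48 to 2.04 |
| 5 | -1.2 to 4.4 |

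A %CAR of 5 means the second challenge softens the enamel by 0.05 x 77 = 3.9 µm, against 77 µm the first time. A small treatment difference does as much damage wherever the mean lies: with a 3-point difference at mean 40, the range is about -7 to 10.

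**Would %NAR do better?** Since %NAR + %CAR = %SMH recovery, %NAR is nearer zero than %CAR whenever it is under half of a positive %SMH recovery. In the table that is 120 - D2 < 17.5, or D2 above 102.5, which covers (118 - 102.5)/25 = 62% of the disagreement window. At D2 = 110, %NAR is 13.0 and %CAR 32.5. %NAR also reaches zero or turns negative once D2 ≥ D1.

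**The case for a change.** The case for a change is that most of this needs no assumption. Two outcomes with the same surname point in opposite directions, no sentence says so, and the analysis section merges them under one term. A few words would remove the risk of a sign error in a validation report. The identity also means that a reader who counts agreement on %SMH recovery, %NAR and %CAR as three confirmations has counted one too many. Restricting inference and the ratio to %NAR would remove both the redundancy and the shrinking denominator.

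The algebra stands in full, and so does the gap in labelling. The step to a changed analysis does not:

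- The plan never claims three independent confirmations.
- A %CAR contrast tests whether the treatment effects on %SMH recovery and %NAR differ. Its variance involves their covariance, so its significance cannot be read off the other two tests, and it is a legitimate separate test.
- Disagreement between the indices is what one should expect: %NAR describes the net state after both challenges, and %CAR the loss at the second relative to the first.
- The ratio and disagreement problems do not coincide in the illustration. Throughout the disagreement window %CAR is at least 8/77 = 10.4, above even the 6.3 limit. It falls below 4.2 only for D2 under about 88.2, where the indices agree.

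**Conclusion.** No change to the plan is called for. The %CAR formula fits its stated comparison and its direction can be read from the definitions. The gaps are in labelling, and analysts would resolve them in the ordinary course of reporting. Both indices bear the name acid resistance and Section 2 lists both, so the term in 7.1 is naturally read as covering the two. Each subject carries exactly four specimens per period, two human in the flange and two bovine in the denture teeth, and 7.1 averages them by location. The remark about a central position is therefore a slip that alters no data.

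Two-sided p-values and the primary significance matching change by nothing. The only substantive alternative, testing %NAR alone and reporting %CAR descriptively, gives no demonstrated gain. Ratio instability specific to %CAR needs a positive-control mean near zero (about 4.2 at an assumed SD of 10, range 2.1 to 6.3), and %NAR is exposed to the same weakness.

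The direction, the identity and the unchanged p-values are exact. The ratio figures rest on assumed R, D2, %CAR means and SDs, because the documents give none. If the observed positive-control mean of either index does turn out close to zero, the ratio's interval will show it, in an analysis the plan already expects to be weak.

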6.4.5 Transverse Microradiography

Sections, approximately 100 µm in thickness, will be cut parallel to the orientation cut (as shown in Figures 2 and 3), after completion of the SMH analysis, using a Silverstone-Taylor Hard Tissue Microtome (Scientific Fabrications Laboratories, USA). The sections will be placed in the TMR-D system and X-rayed at 45 kV and 45 mA at a fixed distance for 12 s. An aluminium step wedge will be X-rayed under identical conditions. The digital images will be analyzed using the TMR software v.3.0.0.18. Sound enamel will be assumed to be 87% v/v mineral.

Lesions will be analyzed after in situ demineralization and the following three parameters calculated:

1. Integrated Mineral Loss - $\Delta Z = [(lesion\ depth \times 87) - area\ under\ the\ curve^*]$
2. Lesion Depth – L (83% mineral i.e. 95% of the mineral content of sound enamel)
3. Maximum mineral density at the surface-zone – SZmax

Note; *area under the curve which relates volume % mineral at distances from the specimen surface with respect to section thickness.

6.5 Laboratory Data

After the analyses are completed, all enamel specimen surface microhardness, transverse microradiography and enamel fluoride uptake data will be reviewed by the principal investigator before transfer to the statistician. The investigator will document this review and documentation will be filed with the laboratory study files.

6.6 Specimen Retention

Laboratory specimens will be retained by the study site for twelve months following database lock.

7. STATISTICAL ANALYSES AND SAMPLE SIZE JUSTIFICATION

7.1 Statistical Analyses

The mean % SMH recovery will be calculated using the five sets of indentations within each enamel specimen. The mean fluoride uptake will be calculated using the four samples within each enamel specimen. The mean % SMH recovery, mean fluoride uptake, mean acid resistance and mean ΔZ , L, SZ_{max} will be computed for the two enamel specimens within a subject for each specimen location (buccal flange or tooth) by treatment; if a subject is missing an enamel specimen, the available enamel specimen will be used. Analyses of fluoride uptake will be performed after using a natural logarithm transformation because the measurements generally are not normally distributed. The validation of the new model will involve two types of evaluations. 1) Analysis level evaluation: The treatments will be compared using analysis of variance models (ANOVA) suitable for a crossover study. The models will include random effects for subject and fixed effects for study period, product, specimen location, and the location-by-product interaction. The random effects will model the correlation and variances over time within a location and the correlation between locations. The primary comparisons of interest will be to determine if the specimens placed in the tooth find the same comparisons to be statistically significant as the specimens placed in the buccal flange. In addition, although likely to be underpowered, the analyses will also include an evaluation of the equivalence of the two locations. This will involve calculating a 95% confidence interval for the ratio between the tooth and buccal flange locations for the relative difference between treatments (treatment difference divided by the positive control mean). A 5% significance level will be used for all tests. No alpha-level adjustments for multiple comparisons adjustments will be applied. 2) Data level evaluation: Agreement between the data from the tooth and buccal flange locations will be evaluated using Bland-Altman plots and intraclass correlation coefficients (ICCs).

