Due to the high cost involved in conducting clinical caries trials a number of surrogate measures of fluoride efficacy have been introduced. These include in situ caries models, rat caries models, in vitro demineralization and remineralization studies, and fluoride uptake studies. These model systems have been extensively reviewed at a Conference held in Rochester, NY in 1994 (Adv Dent Res 9:169-340, 1995). While intra-oral models have been in use for the past forty years, a "Consensus Conference of Intraoral Models" (ADA, Chicago, Sept. 1990) clearly identified the need for validation of intra-oral caries models for their potential use as methods of evaluating the efficacy of fluoride dentifrices and other fluoride-containing dental products. Based on this conference and the Rochester Models conference, there is general agreement among researchers in the field that appropriately validated in situ models represent an acceptable approach for testing the anticaries potential of fluoride products.

Previous work by our group has shown that a modification of the Koulourides intra-oral model (Koulourides et al., 1974) has sufficient sensitivity and reproducibility to respond in dose-response manner to meet the requirements for model validation (Proskin et al., 1992). The model, which uses partially demineralized enamel as the starting hard tissue substrate, permits the evaluation of the ability of the test dentifrice to enhance net remineralization. Our current model has been validated based on its response to different dentifrice fluoride concentrations - 0, 250, 500 and 1100 ppm fluoride (Zero et al., 1994;

Zero, 1995; Zero et al., 2005) as well as in several more commercially funded in situ studies testing fluoride dentifrice products that also included fluoride dose response controls (unpublished data). An additional capability of the model involves testing the acid resistance of remineralized enamel specimens. This test provides the capability to compare the acid resistance of the mineral deposited during the in situ remineralization phase after treatment with different test products.

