The purpose of this study is to evaluate the fluoride dose response of different dentifrice fluoride concentrations - 0, 250, 500 and 1100 ppm fluoride of our existing in situ model involving the use of human enamel specimens placed in the buccal flange area of the subjects partial denture with the modified model involving placement of bovine enamel specimens in a denture tooth location.

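### The purpose is to compare dose response between the two models, but section 7.1 prespecifies no dose contrast and no location-by-dose test, and relies on concordance of significance and on pairwise ratios that are unstable for closely spaced doses

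*Combined protocol and SAP*

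**What the plan says.** Section 1 gives the purpose: "The purpose of this study is to evaluate the fluoride dose response of different dentifrice fluoride concentrations - 0, 250, 500 and 1100 ppm fluoride", for the existing model (human enamel, buccal flange) alongside the modified one (bovine enamel, denture tooth). The same section states how the existing model earned its standing: "Our current model has been validated based on its response to different dentifrice fluoride concentrations - 0, 250, 500 and 1100 ppm fluoride". It also credits the model with being able to "respond in dose-response manner to meet the requirements for model validation".

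The model in section 7.1 has "fixed effects for study period, product, specimen location, and the location-by-product interaction". Product is a four-level factor. No slope, trend contrast or location-by-dose test is named. The interaction is in the model, but no test of it is tied to the objective.

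The primary question in 7.1 is to "determine if the specimens placed in the tooth find the same comparisons to be statistically significant as the specimens placed in the buccal flange". A second evaluation, which the plan itself expects to lack power, consists of "calculating a 95% confidence interval for the ratio between the tooth and buccal flange locations for the relative difference between treatments". Each difference is first divided by the positive control mean. No interval method or margin is given, and the plan does not say which pairs the ratio covers. Bland-Altman plots and ICCs follow at data level.

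**The concern.** Validation rests on dose response, yet no prespecified quantity in 7.1 is a dose-response summary that can be compared between the two locations. Two substitutes carry the conclusion, and each has a weakness.

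- **Concordance of significance.** Two identical models with modest power will often disagree on at least one of six tests by chance. A good tooth model could look discordant, and no prespecified dose-response comparison is there to resolve it.
- **Pairwise ratios.** The flange difference is in the denominator. For neighbouring doses it may be small relative to its error, and the ratio is then close to uninformative.

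At stake is how directly the trial can say whether the modified model keeps the dose response of the existing one.

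**Working it through.** **Inputs.** From section 7.2: 24 completers, SD of between-treatment differences 10 points of % SMH recovery, two-sided 5%. The documents give no expected dose effects and no between-location correlation. Assumed here: effects linear in ppm with a 0-to-1100 difference D of 6 to 30 points, and correlation 0.3 (0 to 0.5 as a range). The positive control mean is taken as well above zero.

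**1. The plan's own figure.** SE of a pair = 10/√24 = 2.04. Noncentrality = 6/2.04 = 2.94. The paired t-test with 23 df gives power 80.4%, so the stated 80% reproduces.

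**2. Pairwise ratios.** A Fieller 95% interval is unbounded when the denominator is not significant at 5%, so P(unbounded) = 1 − power for the flange difference. At a true 6-point difference this is 20% with 23 df, or 17% with the pooled (24−1)(4−1) = 69 df. Under linearity a pair's true difference is D × gap/1100. For example, a 250 ppm gap at D = 15 gives 3.41 points. With 69 df:

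| P(unbounded) | D = 6 | D = 10 | D = 15 |
|---|---|---|---|
| 0-250 and 250-500, each | 90% | 80% | 62% |
| Mean over six pairs | 62% | 38% | 23% |
| 1100-0 alone | 17% | 0.2% | 0% |
| Dose slope | 14% | 0.1% | 0% |

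At larger ranges (23 df), the closest pairs fall to 43% at D = 20 and 11% at D = 30. The six-pair mean falls to 14% and 4% (about 3% at D = 30 with 69 df).

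**3. Concordance.** Simulating two identical models, all six significance verdicts agree in about 17%, 24% and 32-33% of trials at D = 6, 10 and 15 with correlation 0.3. Across correlations 0 to 0.5 the range is about 10-39%.

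**4. What a dose contrast adds.** Within-subject variance = 10²/2 = 50. Doses centred at 462.5 have sum of squares 666,875. SE of the slope per 1100 ppm = 1100 × √(50/(24 × 666,875)) = 1.94, against 2.04 for the 1100-0 pair. For identical models at D = 15 and correlation 0.3, the median Fieller interval is 0.73-1.37 for the slope ratio and 0.72-1.39 for the 1100-0 ratio.

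Now suppose the tooth response is half the flange response, at D = 15 and correlation 0.3. The variance of the tooth-minus-flange difference in a dose mean is 2 × 50 × 0.7/24 = 2.917. The noncentrality is (7.5/1100)² × 666,875/2.917 = 10.63 for both the 3-df interaction and the slope contrast. For the 1100-0 contrast it is 7.5²/(2 × 2.917) = 9.64. Power with 69 error df:

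| Dose shape, correlation | 3-df interaction | 1-df slope | 1-df 1100-0 |
|---|---|---|---|
| Linear, 0.3 | 76% | 90% | 86% |
| Linear, 0 | 59% | 77% | 73% |
| Saturating, 1−exp(−dose/400), 0.3 | 76% | 84% | 86% |

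These power figures are for unscaled contrasts. They ignore sampling error in the positive control means.

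**The case against.** The strongest reply is that the plan already contains a serviceable comparison. Its ratio for 1100 against 0 ppm spans the whole dose range with 1 df, has nearly the precision of a slope, and needs no assumption about shape. Under a saturating curve it is slightly more powerful than the slope. That stands. A reader might infer that the trial could end with no usable statement about dose response; the documents do not support that reading.

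Three further replies also stand.

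- A reader might say the plan never estimates a dose response. It does: four dose means per location with a location-by-product interaction describe the profile without assuming a shape. What is missing is a prespecified contrast or test of it.
- A reader might say the ratio intervals are often unbounded. That depends on effect size, which the documents do not give, and on the Fieller method, which the plan does not name. If a 250 ppm step were worth 6 points, linearity would give D = 6 × 1100/250 = 26.4. The chance would then be about 17-20% for the two closest pairs and near zero for the other four. A delta-method interval is always finite, but unreliable in the same settings.
- The 3-df interaction is not the plan's validation criterion, so 76% against 90% is not a loss relative to what is planned.

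The remark in 7.1 that equivalence is probably underpowered is candid, but it does not supply the missing contrast. Nor does it help the primary criterion, which is where the agreement rates in step 3 apply.

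**Conclusion.** The concern holds in limited form. The stated purpose has no matching prespecified contrast or location-by-dose test. The primary criterion would usually show at least one disagreement between identical models at 6-15 point ranges, with full agreement in only about 17-33% of trials at correlation 0.3. The ratios for 0-250 and 250-500 ppm are unstable at those ranges: a Fieller interval is unbounded 62-90% of the time, and still 17-20% of the time for any pair whose true flange difference is 6 points.

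The 1100-0 ratio is stable once the range reaches about 10 points, and the ratio problem is small near 30 points. The gain from a dose contrast is moderate against the 3-df interaction and small or nil against the 1100-0 pair. Its main value is that it tests the stated purpose directly.

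A reader might also infer that a raw tooth/flange slope ratio is the right measure. Section 1 does not support that: it expects bovine and human enamel to differ quantitatively, so a valid model could show a raw ratio away from 1 through scale alone.

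All figures rest on a linear dose effect unless stated, on the assumed correlation, and on % SMH recovery, the only endpoint with a stated SD.

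**What to change.** In 7.1, analysis level evaluation, add the following from the same mixed model:

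- One prespecified dose contrast per location with scores 0, 250, 500 and 1100 ppm, expressed relative to that location's positive control mean, as the plan already does for treatment differences.
- The 1-df location-by-dose test.
- The tooth/flange ratio of the normalised slopes, with a named interval method (for example Fieller).
- A lack-of-fit check on the dose score.
- The 1100-0 ratio as a companion that assumes no shape.
- All pairwise ratios as supportive results, with the covered pairs listed. Do not restrict them to pairs with a significant flange difference: that selects large denominators and pulls the displayed ratios down.

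State an equivalence margin if the interval is to support a conclusion, and state the scale on which the contrast is formed for log-transformed fluoride uptake.

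The cost is SAP wording and a contrast statement, with no new data, visits or subjects. The downside is reliance on a working dose score, which the lack-of-fit check and the 1100-0 companion are there to guard.
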